3.8.2.2 Injection Site Reactions

Analysis of ISRs will include summaries of the following assessments (defined in Section 3.3.1.1)

- Pain, tenderness, erythema, and induration severity, and lymphadenopathy (categorical variables with grades 1 – 4, and absent).
- Erythema and induration: record the maximum linear diameter
- Blisters, ulceration, necrosis: record the maximum linear diameter and severity

For both of these assessments, the maximum linear diameter will be summarized.

3.8.3 Clinical Laboratory Evaluation

A list of the clinical chemistry, hematology, and coagulation analytes are listed in Table 1.

Quantitative laboratory endpoints will be summarized by time point using descriptive statistics.

3.8.3.1 Hepatic Laboratory Tests: NCI CTCAE Grading

The liver functions test to be summarized via the National Cancer Institute (NCI) Common Terminology Criteria for Adverse Events (CTCAE) criteria are provided in Table 7.

Table 7: CTCAE Grading Criteria for Selected Liver Function Tests

Lab Test	Grade/Criteria			
	1	2	3	4
alanine (ALT)	> 1.0 - 3.0 (x ULN)	>3.0 - 5.0 (x ULN)	>5.0 - 20.0 (x ULN)	> 20.0 (x ULN)
alkaline phosphatase (ALP)	>1.0 - 2.5 (x ULN)	>2.5 - 5.0 (x ULN)	>5.0 - 20.0 (x ULN)	> 20.0 (x ULN)
direct bilirubin	> 1.0 – 1.5 (x ULN)	>1.5 – 3.0 (x ULN)	>3.0 - 10.0 (x ULN)	> 10.0 (x ULN)
gamma-glutamyl transferase (GGT)	>1.0 - 2.5 (x ULN)	>2.5 - 5.0 (x ULN)	>5.0 - 20.0 (x ULN)	>20.0 (x ULN)

Grading criteria based on Common Terminology Criteria for Adverse Events (CTCAE) v4.03

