13.3.4.2.2 HEPATIC ADVERSE EVENTS

Hepatic and biliary AEs and will be summarized separately by system organ class, and preferred term. Liver function tests will be summarized by changes from baseline and graded in severity using the NCI CTCAE criteria.

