13.3.4.2.3 PANCREATIC ENZYME ELEVATIONS

Pancreatic AEs and will be summarized separately by system organ class, and preferred term. Pancreatic elevations will be summarized by changes from baseline and graded in severity using the NCI CTCAE criteria.

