3.1.3 Baseline Value and Change from Baseline (if applicable)

Baseline value is defined as the most recent non-missing value obtained immediately prior to administration of first dose (i.e., generally the study day 1 assessment which occurs pre-dose).

Change from baseline will be calculated by subtracting the baseline value from the post-dose assessment for each patient (i.e. post-dose – baseline). Percent change from baseline will be calculated as $100 \times \text{change score} / \text{baseline score}$.

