3.8.3.2 Pancreatic Enzymes: NCI CTCAE Grading

Amylase and lipase values will be summarized via the NCI CTCAE criteria provided in Table 8.

Table 8: CTCAE Grading Criteria for Selected Pancreatic Enzyme Tests

Lab Test	Grade/Criteria			
	1	2	3	4
amylase	> 1.0 – 1.5 (x ULN)	>1.5 – 2.0 (x ULN)	>2.0 - 5.0 (x ULN)	> 5.0 (x ULN)
lipase	> 1.0 – 1.5 (x ULN)	>1.5 – 2.0 (x ULN)	>2.0 - 5.0 (x ULN)	> 5.0 (x ULN)

Grading criteria based on Common Terminology Criteria for Adverse Events (CTCAE) v4.03

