3.8.5 Vital Signs and Other Physical Findings

Descriptive statistics for vital signs (i.e. heart rate, body temperature, and blood pressure) values and the change from baseline will be presented.

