3.8.6 ECG

Descriptive statistics for ECG parameters (i.e., heart rate (HR), PR interval, RR interval, QRS interval, QT interval, QTcB interval, and QTcF interval) at each assessment time point will be presented for the values and change from baseline scores.

QTc intervals will be calculated using both Fridericia’s and Bazett’s corrections, with the formulae:

$$\text{Fridericia's correction: } QTc = QT/RR^{0.33}$$

$$\text{Bazett's correction: } QTc = QT/RR^{0.5}$$

Additionally, the ECG interpretation categorized as Normal, Abnormal – Clinically Significant, Abnormal – Not Clinically Significant, Not Evaluable, or Not Done will also be provided for each assessment time point (note: ECG interpretations of “Abnormal – Clinically Significant” would be recorded as AEs).

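### The SAP text does not carry over the protocol's change-from-baseline summary for liver tests and pancreatic enzymes, and per-visit grade counts do not link subjects to their own baseline

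*SAP*

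**What the plan says.** **Protocol.** Section 13.3.4.2.2 states: "Liver function tests will be summarized by changes from baseline and graded in severity using the NCI CTCAE criteria". Section 13.3.4.2.3 states: "Pancreatic elevations will be summarized by changes from baseline and graded in severity using the NCI CTCAE criteria". Both sections belong to the analysis of adverse events of special interest.

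**SAP, laboratory tests.** Section 3.8.3 gives the general rule: "Quantitative laboratory endpoints will be summarized by time point using descriptive statistics". Section 3.8.3.1, with its Table 7, covers the liver tests: "The liver functions test to be summarized via the National Cancer Institute (NCI) Common Terminology Criteria for Adverse Events (CTCAE) criteria are provided in Table". Section 3.8.3.2 covers the pancreatic enzymes: "Amylase and lipase values will be summarized via the NCI CTCAE criteria provided in Table 8". Both grading tables use multiples of ULN. None of the three sections mentions change from baseline or a shift table.

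**SAP, other safety data.** Section 3.8.5 says: "Descriptive statistics for vital signs (i.e. heart rate, body temperature, and blood pressure) values and the change from baseline will be presented". Section 3.8.6 says of the ECG parameters that descriptive statistics "at each assessment time point will be presented for the values and change from baseline scores". Section 3.1.3 defines the calculation in general ("Change from baseline will be calculated by subtracting the baseline value from the post-dose assessment for each patient") under a title that limits it to where it applies. Sections 3.9.5.2 and 3.9.5.3 plan shift tables for FACIT-Fatigue items and EQ-5D dimensions.

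**Entry.** Protocol 9.2, criteria 3 and 4, excludes direct bilirubin, ALT or AST above 1.5xULN, and amylase or lipase above 2xULN. It names no limit for ALP or GGT.

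**The concern.** The SAP says in its Section 1 that its procedures follow Section 13 of the protocol. For these two groups of tests it takes up one of the two summaries required there and gives no reason for leaving out the other.

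The missing summary is the one that uses each subject's own starting level. Subjects may enter with values already in Grade 1 or Grade 2, and there is no control arm to show the background rate of abnormal results. A count of grades at a visit treats a subject who was Grade 2 before dosing the same as one who became Grade 2 on treatment. Hepatic and pancreatic findings are of special interest in the protocol (12.1.3.2 and 12.1.3.3), so the report should be able to tell the two cases apart in a prespecified table.

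**Working it through.** The plan gives no figure on this point. Its one design figure, the standard error for LDH change, is 443 x sqrt(2 x (1 - 0.8)) / sqrt(6) = 114.4 U/L. That agrees with the stated 114 and is unaffected.

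**1. Which summary is stated where**

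| Data | Change from baseline | Grade or category |
|---|---|---|
| Liver tests, protocol 13.3.4.2.2 | yes | yes |
| Pancreatic enzymes, protocol 13.3.4.2.3 | yes | yes |
| Liver tests, SAP 3.8.3 and 3.8.3.1 | not stated | yes |
| Pancreatic enzymes, SAP 3.8.3 and 3.8.3.2 | not stated | yes |
| Vital signs, SAP 3.8.5 | yes | none planned |
| ECG, SAP 3.8.6 | yes | yes |

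SAP 3.8.3 cannot be read as covering change from baseline. It repeats the protocol's general laboratory sentence (13.3.4.3), and the protocol asks for change separately for the special-interest tests. SAP 3.1.2 lists the descriptive statistics as n, mean, SD, median, minimum and maximum.

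**2. Highest grade that entry admits** (limits from protocol 9.2, bands from SAP Tables 7 and 8)

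| Test | Highest value at entry | Band | Grade |
|---|---|---|---|
| ALT | 1.5xULN | >1.0 to 3.0 | 1 |
| Direct bilirubin | 1.5xULN | >1.0 to 1.5 | 1 |
| Amylase, lipase | 2.0xULN | >1.5 to 2.0 | 2 |
| ALP, GGT | no limit | n/a | any |

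**3. Steady elevation** (assumed values). One subject with lipase at 1.9xULN throughout is Grade 2 at each visit: 1/8 = 12.5% to 1/6 = 16.7%. With six subjects unchanged at 1.8, 1.2, 0.6, 0.6, 0.8 and 0.8xULN, 2 of 6 are Grade 1 or higher after baseline, and none has worsened.

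**4. Opposite moves** (assumed values, lipase in xULN)
- Before: 1.8, 1.8, 0.6, 0.6, 0.8, 0.8. The sum is 6.4 and the mean 1.07; four subjects are Grade 0 and two Grade 2.
- After: 0.6, 0.6, 1.8, 1.8, 0.8, 0.8. The sum is 6.4 and the mean 1.07; four subjects are Grade 0 and two Grade 2.
- Changes: -1.2, -1.2, +1.2, +1.2, 0, 0. The mean is 0. The SD is sqrt(4 x 1.44 / 5) = sqrt(1.152) = 1.07. The range is -1.2 to +1.2.

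The grade counts and the value means show nothing, and the mean change shows nothing either. The SD and range of the changes do show the moves. A shift table shows two subjects going from Grade 0 to 2 and two from Grade 2 to 0.

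**5. Rises within a band.** ALT from 0.3 to 0.95xULN is 0.95/0.3 = 3.2-fold and never reaches Grade 1. ALT from 1.05 to 3.0xULN is 3.0/1.05 = 2.9-fold and stays Grade 1. Only a within-subject change shows these rises.

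**The case against.** **Much of the information is still there.** SAP 3.8.3 keeps values by visit, the chemistry table (14.3.2.2) covers these analytes, and all data are listed by patient. For 6 to 8 subjects a reader can follow every course by hand. With complete data, the mean change equals the visit mean minus the baseline mean. This stands, and it limits the damage. It does not supply the spread of the changes. Missing values are not imputed (SAP 3.1.4), so if a subject misses a visit the two means no longer describe the same people.

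**The governing SAP may differ.** The post-lock amendment changes Version 3.0 of 22Mar2018. Its table list includes total bilirubin tables, not marked as new, that the SAP body supplied does not have. That body also cites protocol version 1.1 of 20 October 2016, whereas the protocol supplied is Amendment 1 of 17 January 2017. A reader might infer that the sponsor deliberately removed the analysis. The documents do not show that; they show only that the SAP text supplied does not contain it.

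**Table titles prove little.** Neither table list has a title naming a laboratory change or shift table. But the titles for vital signs and ECG do not mention change either, although the text plans it, and the shells are in a separate document. The point therefore rests on the text of 3.8.3 to 3.8.3.2.

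**Pre-existing elevation need not be reported as toxicity.** A reader might infer that it will be. Chemistry is drawn at Screening and Day 1, and nothing says that the grading tables omit baseline. If they include it, a steady lipase of 1.9xULN shows as Grade 2 there too. The TEAE definition also excludes events present at treatment start unless they worsen. What remains is that marginal counts, with or without a baseline column, do not link one subject's visits.

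**The shift table goes beyond the protocol.** This is correct. The protocol requires change from baseline and grading. The shift table is a recommendation, made because mean change alone would also cancel in step 4.

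**Conclusion.** The point holds in a limited form. The SAP text supplied leaves out a summary that the protocol requires for two special-interest groups of tests. The grade counts that it does plan cannot separate an elevation admitted at entry from a rise on treatment within a subject. It would be too strong to say that the tests are graded only against ULN, since values by visit are also planned. It would also be too strong to say that drug effect cannot be separated from baseline, since listings and visit values remain.

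The size is modest. One subject is 12.5% to 16.7% of the study, so a single steady elevation is visible in any grade table. No primary estimate, error rate or sample size changes. The dose and discontinuation rules are applied during treatment and do not depend on these tables.

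The conclusion assumes that the SAP text supplied reflects the plan for these tests in Version 3.0. The entry grades assume that the limits in protocol 9.2 apply to the baseline sample; under SAP 3.1.3 that is generally the Day 1 pre-dose value. The lipase and ALT courses are illustrations, not forecasts. Table 7 as supplied has no AST row; the table may be broken in extraction, so nothing is concluded from that.

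**What to change.** In SAP 3.8.3.1 and 3.8.3.2:

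1. Add change from baseline by visit (n, mean, SD, median, minimum, maximum) for each test in Tables 7 and 8, as protocol 13.3.4.2.2 and 13.3.4.2.3 state.
2. Add a shift table from baseline grade to worst post-baseline grade for each test. Mark as treatment-emergent only a grade above baseline, in line with the TEAE definition in SAP 3.8.1.
3. Keep the planned grading tables 14.3.2.5 and 14.3.2.6, which deliver the grading that the protocol also requires. Add the new tables alongside them.

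The database is already locked, so a further addendum is the practical route. It can cite the protocol as the prespecification for item 1 and should label item 2 as added after lock. If Version 3.0 or its shells already contain item 1, a reference to them is enough for that part.

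The cost is a few lines of SAP text and a few tables from chemistry already scheduled at every visit. No assessment, dose rule or stopping rule changes.

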3.8.3.2 Pancreatic Enzymes: NCI CTCAE Grading

Amylase and lipase values will be summarized via the NCI CTCAE criteria provided in Table 8.

Table 8: CTCAE Grading Criteria for Selected Pancreatic Enzyme Tests

Lab Test	Grade/Criteria			
	1	2	3	4
amylase	> 1.0 – 1.5 (x ULN)	>1.5 – 2.0 (x ULN)	>2.0 - 5.0 (x ULN)	> 5.0 (x ULN)
lipase	> 1.0 – 1.5 (x ULN)	>1.5 – 2.0 (x ULN)	>2.0 - 5.0 (x ULN)	> 5.0 (x ULN)

Grading criteria based on Common Terminology Criteria for Adverse Events (CTCAE) v4.03

3.8.4 Anti-drug antibodies

The number and percentage of patients with a positive confirmatory assay will be summarized for each of the scheduled assessment time points.

3.8.5 Vital Signs and Other Physical Findings

Descriptive statistics for vital signs (i.e. heart rate, body temperature, and blood pressure) values and the change from baseline will be presented.

3.8.6 ECG

Descriptive statistics for ECG parameters (i.e., heart rate (HR), PR interval, RR interval, QRS interval, QT interval, QTcB interval, and QTcF interval) at each assessment time point will be presented for the values and change from baseline scores.

QTc intervals will be calculated using both Fridericia’s and Bazett’s corrections, with the formulae:

$$\text{Fridericia's correction: } QTc = QT/RR^{0.33}$$

$$\text{Bazett's correction: } QTc = QT/RR^{0.5}$$

Additionally, the ECG interpretation categorized as Normal, Abnormal – Clinically Significant, Abnormal – Not Clinically Significant, Not Evaluable, or Not Done will also be provided for each assessment time point (note: ECG interpretations of “Abnormal – Clinically Significant” would be recorded as AEs).

3.8.7 Physical Examination

The complete set physical examination findings will be provided in listings. Clinically significant physical examination abnormalities will be included and summarized as AEs if appropriate.

3.9 Efficacy Analysis

3.9.1 Primary Efficacy Endpoint Analysis

The primary evaluation period is from Week 6 to Week 12. The primary efficacy endpoint is the change from baseline in serum LDH levels during this period, defined as the mean of the non-missing LDH values of Weeks 6, 8, 10, and 12 minus the baseline LDH value (defined in Section 3.1.3).

The primary efficacy endpoint analysis will be a Wilcoxon signed-rank test on the change from baseline endpoints.

Summary statistics and will be provided for patient's mean LDH value, change from baseline scores, and percent change from baseline scores over the primary evaluation period.

Additionally, summary statistics for the values, change, percent change from baseline scores, and the two-sided Wilcoxon signed-rank test will be performed at each post-baseline assessment time-point.

3.9.2 Secondary Efficacy Endpoints Analysis

Secondary efficacy endpoints include the change from baseline values at each of the following scheduled post-baseline assessment time-points:

- total hemoglobin,
- free hemoglobin,
- haptoglobin,
- reticulocytes
- hemoglobinuria (note: hemoglobinuria will be assessed using a urine colorimetric scoring system).

The change from baseline for each of these endpoints will be assessed by a two-sided Wilcoxon signed-rank test. Additionally, the summary statistics will be presented for the values, change, and percent change from baseline scores.

Additionally, the secondary endpoint of an LDH score $< 1.5 \times \text{ULN}$ (i.e., a dichotomous endpoint) will be assessed at the primary evaluation period and the scheduled post-baseline assessment time-points by means of a one-sided exact McNemar's test.

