7.2.2 EFFICACY

Primary efficacy:

- The primary evaluation period is from Week 6 to Week 12. The primary efficacy endpoint is the change-from-baseline in serum LDH levels during this period, defined as the mean LDH values of Weeks 6, 8, 10, and 12 minus the baseline value of LDH.

Secondary efficacy:

- Changes from baseline in LDH, total bilirubin, total hemoglobin, free hemoglobin, haptoglobin, reticulocytes, and hemoglobinuria, at each of the scheduled post-baseline assessment time-points.

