2.2.3.7 Urinalysis

A urinalysis will be performed to measure pH, specific gravity, protein (qualitative), glucose (qualitative), ketones (qualitative), bilirubin (qualitative), urobilinogen, occult blood, hemoglobin, and cells. A microscopic examination will be performed, if necessary. Hemoglobinuria will be assessed using a urine colorimetric scoring system.

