3.1.2 Reporting of Numerical Values

All clinical study data will be presented in patient data listings. Descriptive statistics (n, mean, standard deviation, median, minimum, and maximum) will be calculated by treatment group for continuous variables. Confidence intervals will be provided where appropriate. For continuous endpoints, the confidence interval for the mean will be based on the t-distribution (e.g., CLM in the SAS Proc Means procedure).

Frequencies and percentages will be presented by treatment group for categorical and ordinal variables. If there are missing values, the number of missing values will be presented, but without a percentage and the number of non-missing values used as the denominator.

Means, medians, standard deviations, and confidence intervals will be reported to one decimal place more than the data reported on the CRF or by the laboratory/vendor. Minimum and maximum will be reported to the same number of decimal places displayed on the CRF or by the laboratory/vendor. P-values will be reported to 4 decimal places.

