3.1.4 Handling of Missing/Incomplete Values

Unless otherwise explicitly specified, missing data will not be imputed; observed cases will be used in the analyses.

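### SAP 3.9.2 plans percent change for hemoglobinuria, a urine colour score, so the percentage depends on how the levels are numbered

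*SAP*

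**What the plan says.** Protocol 7.2.2 defines the secondary efficacy endpoints on the change scale only: "Changes from baseline in LDH, total bilirubin, total hemoglobin, free hemoglobin, haptoglobin, reticulocytes, and hemoglobinuria, at each of the scheduled post-baseline assessment time-points". Percent change is added by the SAP.

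SAP 3.9.2 lists total hemoglobin, free hemoglobin, haptoglobin, reticulocytes and hemoglobinuria, with a note on the last that "hemoglobinuria will be assessed using a urine colorimetric scoring system". It then sets the test, "The change from baseline for each of these endpoints will be assessed by a two-sided Wilcoxon signed-rank test", and the descriptive output, "Additionally, the summary statistics will be presented for the values, change, and percent change from baseline scores". None of the five is exempted from percent change.

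SAP 3.1.3 supplies the formula: "Percent change from baseline will be calculated as" 100 × change score / baseline score. SAP 3.1.4 says that, unless specified otherwise, "missing data will not be imputed; observed cases will be used in the analyses". Neither section has a rule for a baseline of zero.

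The colour score is mentioned again in SAP 2.2.3.7 and in Protocol 11.2.7.2. Neither place gives the number of levels or the value of the lowest one.

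**The concern.** A percentage of baseline is meaningful when zero on the scale means none of the quantity and the units are equal. A colour score gives ordered levels with labels. Renumbering the labels leaves each subject's change as it was but alters the divisor, so the percent change reflects a coding choice as well as the urine findings.

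There is a second, conditional problem. If clear urine is coded 0, percent change is undefined for a subject with clear urine at baseline, and under the observed-case rule that subject leaves the percent-change summary. Such subjects can enrol: inclusion criterion 4 (Protocol 9.1) asks for raised LDH or a known C5 mutation, not for hemoglobinuria. On a score where lower is better they can only stay the same or worsen, so the summary would keep only those with room to improve.

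At stake is one descriptive column in the hemoglobinuria tables, which are planned for four analysis populations.

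**Working it through.** The plan states no figure for hemoglobinuria. Its one design figure, the LDH standard error in SAP 3.11, does reproduce (443 × √(2 × (1 − 0.8)) / √6 = 114.4 U/L against about 114), but it has no bearing here.

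**Inputs from the documents.** The percent-change formula (SAP 3.1.3), the observed-case rule (SAP 3.1.4), and planned enrolment of about 6-8 (SAP 2.2.1). **Assumed.** The colour levels are consecutive integers, lower is better, and all subject data below are invented for illustration.

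**1. Effect of numbering on one subject.** For baseline b and later value y, percent change is 100 × (y − b)/b. Adding a constant k to every level gives 100 × (y − b)/(b + k): the numerator is unchanged and the divisor is not. For a two-step improvement:

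| Numbered from 0 | Percent | Same levels numbered from 1 | Percent |
|---|---|---|---|
| 2 to 0 | −2/2 = −100% | 3 to 1 | −2/3 = −66.7% |
| 4 to 2 | −2/4 = −50% | 5 to 3 | −2/5 = −40% |
| 6 to 4 | −2/6 = −33.3% | 7 to 5 | −2/7 = −28.6% |

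The gap is widest for subjects who start near the bottom of the scale.

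**2. Effect on a group of six.** Take baselines 0, 0, 1, 2, 4, 6 and later values 1, 0, 0, 1, 2, 3.

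- Mean absolute change: (1 + 0 − 1 − 1 − 2 − 3)/6 = −1.0, under either numbering.
- Numbered from 0: two subjects are undefined. The other four give −100, −50, −50 and −50, so the mean is −250/4 = −62.5% and the median −50% (n = 4).
- Numbered from 1: all six are defined, at +100, 0, −50, −33.3, −40 and −42.9. The mean is −66.2/6 = −11.0% and the median −36.7% (n = 6).

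The mean moves from −62.5% to −11.0% with no change in the urine findings, and the median moves as well.

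**3. Effect of a zero level, if there is one.** Take six subjects: three go from 4 to 2, two stay at 0, one goes from 0 to 4. Percent change is defined in three, each −50%, so the summary reads −50% (n = 3). The mean absolute change in all six is (−2 − 2 − 2 + 0 + 0 + 4)/6 = −0.33. Each subject lost is 1/6 = 17% of a sample of six, or 1/8 = 12.5% of eight.

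**4. The SAP's own practice for ordered scores.** FACIT-Fatigue items (SAP 3.9.5.2) and EQ-5D dimensions (SAP 3.9.5.3) get values, change from baseline and shift tables. Neither section plans percent change. Hemoglobinuria in 3.9.2 gets percent change and no shift table.

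**The case against.** The strongest reply is that little depends on this column. The protocol endpoint is absolute change, and so is the quantity tested. A subject with an undefined percentage stays in the values, the absolute change and the Wilcoxon test. SAP 3.1.2 requires n, median, minimum and maximum beside the mean, and all data are listed by patient, so with 6-8 subjects a reduced n or an extreme value would be visible. All of this stands, and it keeps the point minor. It does not answer the numbering problem, because the median moves with the numbering too.

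A second reply is that the text may have moved on. The post-lock amendment names SAP Version 3.0 as the latest, its table list differs from the one in the SAP body, and the shells are a separate document. A footnote or exemption could exist there. The amendment supplied here does not list one among its changes.

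A reader might also infer that percent change must go for haptoglobin and free hemoglobin, on the view that their baselines lie near zero. The arithmetic risk exists. In an assumed set of six, five subjects go from 50 to 40 and one rises by 10 units. The mean percent change runs from (5 × −20 + 20)/6 = −13.3% when that subject starts at 50 to (5 × −20 + 2000)/6 = +316.7% when the start is 0.5. But the median stays at −20% and the mean absolute change at −6.67, and the documents give no baselines, units or reporting limits for either analyte. Nor would one direction of bias hold for all three variables: a subject at the floor can only stay or rise, and whether a rise is good or bad differs by analyte.

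Finally, a reader might take 3.9.2 to apply percent change to every secondary endpoint. It does not: LDH below 1.5×ULN is dichotomous and is assessed by McNemar's test.

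**Conclusion.** The point holds for hemoglobinuria. Percent change of a colour score whose numbering is not stated is an arbitrary statistic: −50% or −40% for the same two-step improvement, and −62.5% or −11.0% for the same six assumed subjects. This rests only on the score being a set of ordered levels, which is how the plan describes it.

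The loss of subjects with clear urine at baseline is conditional on a zero level, which the documents neither state nor exclude. If the scale starts at 1, nobody is lost.

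The documents do not support removing percent change for haptoglobin or free hemoglobin. For these, the planned absolute change and median are enough, with a count of undefined percentages.

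This is a minor matter of descriptive reporting. No planned test, protocol endpoint or stated design figure changes.

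**What to change.** In SAP 3.9.2, exclude hemoglobinuria from the percent-change summaries and add a shift table from baseline to each scheduled visit, in the form already planned for FACIT-Fatigue items and EQ-5D dimensions. Keep the values, the absolute change and the Wilcoxon test. Make the same change in the hemoglobinuria tables (14.2.6.1 to 14.2.6.4 in the SAP body's list, 14.2.7.1 to 14.2.7.4 in the post-lock list). If it is made after database lock, label it as a post-lock change.

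For haptoglobin and free hemoglobin, leave percent change in place, rely on the absolute change and the median, and show how many subjects have an undefined percentage.

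The cost is a sentence or two of SAP text and edits to the table shells. One descriptive column for hemoglobinuria is lost; nothing that the protocol requires is removed.
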